NUMBER OF VOLUNTEERS AND STATISTICAL ANALYSIS PLAN

The primary endpoint:

ST/HR index during ETTs at the early and late follicular phases of the menstrual cycle
(μ V/beat per minute (bpm))

The secondary endpoints:

1. Change in maximal exercise capacity with exercise and menstrual cycle (METs score)
2. maximum ST segment depression (mm)
3. Relationship of blood pressure and heart rate changes with exercise and menstrual cycle
4. ST/HR slope (μ V/beat per minute (bpm))
5. The change in high-sensitive cardiac troponin T after ETT (ng/L)
6. Hormone levels (estrogen, progesterone, FSH, LH) at the early and late follicular phases of the menstrual cycle

Definition of the endpoints:

The primary endpoint will be the ST/HR (heart rate) index (μ V/bpm) in ETT. The ST/HR index (μ V/bpm) is automatically generated by the General Electronic GE Healthcare T2100-ST Treadmill & CASE 6.73 Stress Test System. The secondary endpoints will be the change in hs cTnI between the before and after ETT, maximal exercise capacity (METs score), ST/HR slope (μ V/bpm), maximal horizontal or down slope ST segment depression (mm) with exercise. Secondary end points other than cTnI are automatically generated by the General Electronic GE Healthcare T2100-ST Treadmill & CASE 6.73 Stress Test System.

The null hypothesis

There is no difference between in the ST/HR index (μ V/bpm) between the menstrual phases.

The study power

The power is calculated to prove the alternative hypothesis in which there is a 50 % difference between the ETT ST/HR index (μ V/bpm). In a paired study sample, with type I error of 5 % and

type II error of 20 %, the sample size is calculated as 34 patients.

The statistical tests

All statistical tests are performed using the Statistical Package for the Social Sciences 25.0 for Windows (SPSS Inc., Chicago, IL, USA). The sample size is determined using the G-power program, according to the study's effect size, type 1 error, and power. Type error is 5%, the power of the study is 80%, and effect size has not been previously reported in the literature. Assuming a 50% difference in the primary endpoint between the early and late follicular phases (effect size: 0.5), the number of premenopausal female patients needed to be enrolled is 34.

Kolmogorov-Smirnov or Shapiro-Wilk test is used to analyze the normality of the data. Numerical data with normal distribution are expressed as mean \pm SD, parameters with skewed distribution are expressed as median (min-max or interquartile range (IQR)), while categorical data are expressed as percentages (%). A comparison of categorical data between the groups is made with the chi-square test. In addition, a comparison of numerical data before and after menstruation is made using the paired samples T-test and/or Wilcoxon test, depending on the distribution of the data. A 2-sided p-value of <0.05 is accepted as statistical significance.

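### The sample size treats a 50% difference in ST/HR index as a standardized effect size of 0.5, so the stated 80% power for a 50% difference has no basis

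*SAP*

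**What the plan says.** The SAP gives the sample size twice. Under the study power, the alternative hypothesis is one "in which there is a 50 % difference between the ETT ST/HR index"; for a paired sample with 5% type I error, the text continues "type II error of 20 %, the sample size is calculated as 34 patients". Under the statistical tests, G*Power is named as the program, driven by effect size, type I error and power. That paragraph concedes that the "effect size has not been previously reported in the literature" and then writes "Assuming a 50% difference in the primary endpoint between the early and late follicular phases (effect size: 0.5", closing with "the number of premenopausal female patients needed to be enrolled is 34".

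The planned comparison is "the paired samples T-test and/or Wilcoxon test, depending on the distribution of the data", and significance is two-sided at 5%. The Protocol contains no sample-size text. Neither document states an expected mean ST/HR index, an SD in either phase, a within-woman correlation or an SD of the paired differences.

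**The concern.** The effect size that G*Power uses for a paired t-test is dz, the mean paired difference divided by the SD of the within-woman differences. A 50% difference is a fraction of a mean. The SAP's parenthesis sets one equal to the other, apparently because both can be written as 0.5.

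This is the only justification given for the sample size on the primary endpoint. A reader of a null result would take from it that the study had 80% power against a 50% change in ST/HR index between phases. Nothing in the plan supports that reading. The change that 34 pairs can detect could be well below or well above 50%.

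**Working it through.** **Inputs from the SAP.** Alpha 0.05; two-sided (stated for the analysis, while the sample-size text gives no sidedness); power 80%; paired design; effect size 0.5; stated n = 34.

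**Step 1: reproduce 34.** For a paired t-test, dz = (mean difference) / (SD of differences). Power comes from the noncentral t distribution with n − 1 degrees of freedom and noncentrality dz × √n. At dz = 0.5:

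- n = 33: noncentrality 0.5 × √33 = 2.872, critical t 2.037, power 79.5%
- n = 34: noncentrality 0.5 × √34 = 2.915, critical t 2.035, power 80.8%

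So 34 is the smallest n that reaches 80%. The obvious alternatives do not return 34: a one-sided t-test gives 27, the two-sided normal approximation gives 32, and the two-sided Wilcoxon test gives 35 (asymptotic relative efficiency 3/π) or 39 (minimum efficiency 0.864). The value entered was therefore almost certainly dz = 0.5.

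**Step 2: what a 50% difference implies.** Let k = (SD of within-woman differences) / (reference mean ST/HR index). A 50% relative difference is 0.5 × mean, so

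dz = (0.5 × mean) / (k × mean) = 0.5 / k.

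This equals 0.5 only when k = 1. With equal SDs in both phases, k = CV × √(2(1 − r)), where CV is the between-woman coefficient of variation and r is the correlation between phases. At an assumed r = 0.5 this reduces to k = CV, so the SAP's equation would then need a CV of 100%.

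**Step 3: range over k.** The documents give nothing that favours any value of k, so the values below are assumptions. Columns 3 and 4 take a true 50% difference. The last column is the relative difference that 34 pairs detect with exactly 80% power: the dz that gives 80% at n = 34 is 0.495, multiplied by k.

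| k (assumed) | dz for a 50% difference | Pairs needed for 80% | Power with 34 pairs | Difference detectable with 34 pairs |
|---|---|---|---|---|
| 0.5 | 1.00 | 10 | >99.9% | 24.8% |
| 0.75 | 0.67 | 20 | 96.5% | 37.1% |
| 1.0 | 0.50 | 34 | 80.8% | 49.5% |
| 1.25 | 0.40 | 52 | 62.0% | 61.9% |
| 1.5 | 0.33 | 73 | 47.1% | 74.3% |
| 2.0 | 0.25 | 128 | 29.3% | 99.0% |

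**Step 4: the alternative test.** If the Wilcoxon signed-rank test is used on normally distributed differences at dz = 0.5, 34 pairs give about 79% power, by simulation and by the 3/π efficiency. This is a side detail and does not affect the main point.

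**The case against.** The strongest case for the plan is that 0.5 is a familiar conventional effect size, that the SAP openly says no prior value exists, and that the parenthesis may be meant to define the 50%, as loose wording for half an SD. On that reading the calculation is sound and only a label is wrong. No participant, analysis or estimate is shown to be affected, the direction of any error is unknown, and the span from 10 to 128 pairs comes entirely from an assumed range of k.

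Much of this stands. Using 0.5 as an assumption is legitimate, 34 follows from it, and the table illustrates sensitivity without measuring an actual error. The half-an-SD reading, however, does not fit the study-power paragraph, which gives the 50% difference in the ST/HR index with no reference to an effect size and reads naturally as a relative difference. If half an SD was what the sponsor meant, the correction below says exactly that.

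It is also fair to say that deleting the 50% makes the statement accurate without giving 0.5 any meaning in μV/bpm. Only an assumed mean and SD would do that, and the documents supply neither.

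**Conclusion.** The concern holds. 34 complete pairs give about 80% power (80.8% by paired t-test, two-sided 5%) for a mean difference of half an SD of the within-woman differences. The SAP's claim of 80% power for a 50% difference in ST/HR index does not follow from anything in either document. It would be right only if the SD of the differences happened to equal the reference mean.

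For a true 50% difference, 34 pairs could be far more than needed or far too few: with k assumed between 0.5 and 2.0, power runs from above 99.9% to 29.3%. No loss of power is claimed, and no single corrected sample size can be computed. The fault lies in the conversion from 50% to 0.5; the step from 0.5 to 34 is correct. It should be corrected because it is the only power statement for the primary endpoint.

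**What to change.** Revise both sample-size statements in the SAP (the study power and the statistical tests) so that they agree. Suggested text:

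> An effect size of 0.5 is assumed. 34 women completing both ETTs give about 80% power (paired t-test, two-sided 5%; about 79% if the Wilcoxon test is used on normally distributed differences) to detect a mean paired difference in ST/HR index of 0.5 SD of the within-woman differences.

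Delete the 50% claim. Alternatively, keep it only with an explicit assumed mean and SD of differences in μV/bpm, labelled as assumptions, and with the power range that results.

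A minor clarification is included: the number refers to women who complete both tests, whereas the SAP now refers to enrolment. The documents give no loss rate, so no enrolment figure is proposed; one lost pair would take t-test power only to 79.5%.

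The cost is a rewording in two places. Sample size, endpoint, test and alpha are unchanged. The stated sensitivity is no longer a percentage of ST/HR index unless the sponsor adds an assumed mean and SD.

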1. OBJECTIVE AND HYPOTHESES

Objective: To compare exercise treadmill test (ETT) results in premenopausal women at the early and late follicular phases of the menstrual cycle.

General Hypothesis:

False positive results are commonly observed in women after exercise treadmill test (ETT). The studies report severe variability in the sensitivity and specificity of ETT in detecting significant coronary artery disease (CAD). Sensitivity ranges from 23% to 100% and specificity ranges from 17% to 100% (1, 2). ETT utilizes electrocardiography (ECG) along with heart rate (HR) and blood pressure (BP) monitoring during exercise, typically involving a treadmill. The major finding of ETT is the ST segment deviation from the baseline. False positive stress ECGs are common especially in premenopausal women, limiting the specificity of the test (3-6).

Menstrual periods can cause biological variability in ETT in premenopausal women (7). The menstrual period is divided into phases: early follicular (days 1-5), late follicular (days 6-12), ovulation (days 13-15), early luteal (days 16-19), mid-luteal (days 20-23) and late luteal phases (24-28 days). Early follicular phase is characterized by low estrogen and low progesterone, late follicular phase is characterized by low progesterone and high estrogen. Mid-luteal phase is characterized by high progesterone and high estrogen levels (7-9). Early and late follicular phases of the menstrual cycle in women demonstrate nearly 4 fold differences in estrogen levels. The menstrual period phase affects thermoregulation and physical working capacity in women (9, 10). Estrogen has protective and vasodilatory effects on the cardiovascular system (11). With the discovery of high sensitive cardiac troponins (hs-cTn), minute changes of hs-cTn have become detectable (12).

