The effects of menstrual periodic changes on the results of exercise treadmill test in premenopausal women have not been clearly defined. Primary purpose of the study is to investigate the biological causes of false positive test results in the treadmill exercise test in premenopausal women. Estrogen is known to have direct vasodilatory effects on coronary arteries. Early and late follicular phases of the menstrual cycle are characterized by low and high estrogen levels, respectively. The Early Follicular Phase starts on the first day of the menstrual cycle and ends when oestradiol begins to increase. It is characterised by increasing LH and FSH and constant low levels of oestradiol. The late follicular phase starts with the increase in oestradiol and ends at its preovulatory peak (7-10). False positive stress ECGs are commonly reported especially in premenopausal women, limiting the specificity of the ETT (3-5). Studies demonstrated that HR adjustment of in exercise-induced ST segment depression using the ST/HR slope or ST/HR index could improve the sensitivity and specificity of ETT (2, 13-15).

The hypothesis of the study is that ETT results and hs-cTnT release after ETT will change at the early and late follicular phases in premenstrual women.

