2. STUDY ENDPOINTS

The major finding of ETT is the ST segment deviation from the baseline. The ST segments are evaluated 60-80 ms after the J point. ECG positive ETT result was defined as ≥ 1 mm (0.1 mV) horizontal or downsloping ST depression in at least 3 consecutive beats.

Chest pain or inadequate hemodynamic response during ETTs are considered clinically positive ETT result. Tests that do not meet these criteria but show ST segment changes or had low diagnostic value due to baseline ECG changes are considered indeterminate ETT results.

Automated measurements and mathematical calculations are recorded in the ETT system (General Electronic GE Healthcare T2100-ST Treadmill & CASE 6.73 Stress Test System).

ETT results are evaluated by 2 different cardiologists and categorized as positive/indeterminate/negative ETT results.

Hs-cTn is measured before and 15 minutes after ETT.

Indices of ST/HR slope and the ST/HR index were reported automatically by the General Electronic GE Healthcare T2100-ST Treadmill & CASE 6.73 Stress Test System device. The primary endpoint in the study was the ST/HR index. The secondary endpoints were ST/HR slope, maximum ST segment depression (mm), HR and BP response to exercise, maximum exercise capacity, and the change in hormones and hs-cTn after ETT.

Primary endpoint:

ST/HR index during ETTs at the early and late follicular phases of the menstrual cycle

(μ V/beat per minute (bpm))

Secondary endpoints:

1. Change in maximal exercise capacity with exercise and menstrual cycle (METs score)
2. Maximum ST segment depression (mm)
3. ST/HR slope (μ V/beat per minute (bpm))
4. The change in high-sensitive cardiac troponin T after ETT (ng/L)
5. Hormone levels (estrogen) at the early and late follicular phases of the menstrual cycle

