The early and late follicular phases are determined from the history. The early follicular phase ETT is planned on the 3rd day of menstrual bleeding, while the menstrual bleeding continues. The late follicular phase ETT is planned on the 3rd day after the menstrual bleeding ends. Hormone levels are measured before each ETT to ascertain the phase of the menstrual cycle. Two ETTs are performed on each participant.

The blood sample is taken 30 minutes before the ETT to measure follicular stimulating hormone (FSH), luteinizing hormone (LH), estrogen, progesterone, and hs-cTn. After the test, the patient is allowed to rest for 15 minutes and blood is taken to check the 2nd hs-cTn after ETT.

Sampling Method: Probability Sample

Minimum Age: 20 years

Maximum Age: 55 years

Sex: Female

Gender Based: Yes

Female patients in the pre-menopausal period

The inclusion criteria are:

1. Premenopausal female patients with regular menstrual cycles,
2. ages between 20-55,
3. Patients have been seen in the cardiology clinic by a cardiologist for the symptoms of chest pain with a clinical suspicion of angina or angina equivalent.
4. A cardiologist has ordered ETT as a diagnostic test for the symptoms of chest independent of the study protocol
5. Patients can understand and sign the informed consent.

[figure not shown]
The exclusion criteria are:

1. Women with menopause or menopause-related symptoms or menstrual cycle irregularity or use of hormonal therapy or oral contraceptives, current pregnancy
2. patients with a history of CAD,
3. secondary or uncontrolled hypertension,
4. history of valvular heart disease,
5. left ventricular hypertrophy on echocardiography,
6. abnormal systolic or diastolic function or wall motion abnormality on echocardiography,
7. history of cardiac arrhythmia or heart failure, pericarditis or myocarditis
8. history of cancer, stage ≥ 3 kidney failure, liver failure, history of psychiatric illness, history of, recent infection.
9. pre-existing ECG abnormality that would confound the interpretation during the ETT (baseline ECG was considered abnormal in the presence of the following findings: prolonged QT interval, chamber hypertrophy, alterations in the ST-T waves, any degree of heart block, T-wave abnormalities, premature ventricular contractions (PVCs), right bundle branch block (RBBB), left bundle branch block (LBBB), left or right axis deviation, or any abnormal rhythm other than normal sinus rhythm).

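### The only test the SAP names for categorical data is chi-square between groups, although the ETT category is recorded twice in the same women; a paired test should be named (minor).

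*SAP*

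**What the plan says.** The last paragraph of the SAP, under the statistical tests, has one sentence for categorical data: "A comparison of categorical data between the groups is made with the chi-square test". The next sentence turns to numerical data and names paired methods: "a comparison of numerical data before and after menstruation is made using the paired samples T-test and/or Wilcoxon test". Neither document names a paired method for categories, and the SAP does not say what the groups are.

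The design is paired throughout. Protocol section 3 states "Two ETTs are performed on each participant", and the SAP's power paragraph assumes the same: "In a paired study sample, with type I error of 5 % and".

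Protocol section 2 creates a categorical outcome at each phase: "ETT results are evaluated by 2 different cardiologists and categorized as positive/indeterminate/negative ETT results". That category appears in neither numbered endpoint list. The Protocol's objective in section 1 is "To compare exercise treadmill test (ETT) results in premenopausal women at the early and late follicular phases of the menstrual cycle", and its hypothesis is worded in the same general terms: "The hypothesis of the study is that ETT results and hs-cTnT release after ETT will change at the early and late follicular phases".

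**The concern.** The only comparison the documents define is early against late follicular phase in the same women. Each woman therefore contributes two linked categories, and the one categorical test on offer is the standard test for independent samples. There are two ways to read the rule:

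- If the groups are the two phases, chi-square ignores the pairing.
- If the groups are something else, the phase comparison of ETT categories has no named test.

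On either reading no paired test is specified, although the SAP respects the pairing for numerical data one sentence later. At stake are the p-value and confidence interval for any statement that positivity differs between phases. A real shift could be missed, or the test could be chosen after the results are seen.

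**Working it through.** **Inputs.** From the documents: 34 women, two ETTs each, two-sided 5% level. Not in the documents, so assumed: the proportion positive at each phase (p1, p2) and the within-woman correlation phi. For the 2x2 case the result is collapsed to positive versus not positive.

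**The plan's own figure.** A two-sided paired t-test with standardised difference 0.5, alpha 5% and power 80% needs 34 women (power 80.8%); the normal approximation gives (1.96 + 0.84)²/0.5² = 31.4, so 32. The stated N = 34 is reproduced. It rests on the numerical primary endpoint and does not depend on the categorical test.

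**Why chi-square is conservative here.** The true variance of the difference in proportions is

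[p1(1 − p1) + p2(1 − p2) − 2·phi·√(p1(1 − p1)p2(1 − p2))]/n.

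Chi-square omits the last term. With p1 = p2 the true variance is (1 − phi) times the variance assumed, so the approximate rejection rate is 2[1 − Φ(1.96/√(1 − phi))]:

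- phi 0.3: 1.96/0.837 = 2.34, giving about 1.9%
- phi 0.5: 1.96/0.707 = 2.77, giving about 0.6%

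In the same way an unpaired interval is too wide by 1/√(1 − phi): about 1.20 times at phi 0.3 and 1.41 times at phi 0.5.

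**Exact enumeration.** All paired 2x2 tables at n = 34, with uncorrected chi-square on the margins against three forms of McNemar's test. Percentage of tables giving p < 0.05:

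| Positive, phase A v B | phi | Chi-square | Ordinary McNemar | Mid-p | Exact |
|---|---|---|---|---|---|
| 30% v 30% (no change) | 0 | 5.4 | 4.6 | 4.6 | 2.7 |
| | 0.3 | 2.2 | 4.3 | 4.1 | 2.2 |
| | 0.5 | 0.7 | 4.6 | 3.6 | 1.7 |
| 40% v 20% | 0 | 46 | 42 | 42 | 33 |
| | 0.3 | 45 | 54 | 54 | 44 |
| | 0.5 | 43 | 73 | 70 | 58 |
| 20% v 10% | 0.3 | 17 | 25 | 22 | 13 |
| 15% v 5% | 0 | 30 | 26 | 22 | 13 |
| | 0.3 | 26 | 35 | 24 | 13 |
| 10% v 5% | 0.3 | 8 | 12 | 5 | 2 |

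Ordinary McNemar held its null rejection rate at 4.3 to 4.8% for 30% and 15% positivity with phi 0 to 0.5.

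**One illustrative table**, chosen so that the tests fall on either side of 0.05. It shows what can happen, not what is likely. Eight women are positive at both phases, 8 at one phase only, 1 at the other only, and 17 at neither, so 16/34 v 9/34 are positive (phi 0.50).

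- Chi-square: 68(16·25 − 9·18)²/(34·34·25·43) = 3.10, p = 0.078.
- Ordinary McNemar: (8 − 1)²/9 = 5.44, p = 0.020. Exact: 2(1 + 9)/512 = 0.039. Mid-p: (2 + 9)/512 = 0.021.
- Observed difference: 7/34 = 20.6 points.
- Unpaired 95% CI: 0.206 ± 1.96 × 0.114, or −1.8 to 43.0 points.
- Paired 95% CI (adjusted Wald): (9 − 2)/36 ± 1.96 × 0.0862, or 2.5 to 36.3 points.

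**The case against.** The case for leaving this alone has real weight.

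- **No listed endpoint is touched.** Every numbered endpoint is numerical, paired tests are named for numerical data, and the SAP's null hypothesis concerns only the ST/HR index. This stands and is why the point is minor. It does not remove the point: the category is defined in the endpoints section, and the SAP chose to give a rule for categorical data.
- **Misuse is not stated.** No sentence says chi-square will compare the phases, and the term could loosely cover McNemar's chi-square. That is possible, but comparing groups, set beside a separate paired sentence for numerical data, does not say so. If McNemar was meant, one word settles it.
- **The figures rest on assumed rates and correlations.** True. The direction under positive correlation follows from the variance formula; the size is unknown.

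Stronger readings are tempting, and the documents do not support them.

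- A reader might link the category to "Primary purpose of the study is to investigate the biological causes of false positive test results in the treadmill exercise test" and conclude that the main question is being analysed wrongly. A false positive needs a reference standard for coronary disease, and the text of neither document schedules one. The category measures positivity, and the documents do not say that ETT results in the objective means this category.
- A reader might expect spurious significance. With positive correlation the error is in the conservative direction.
- A reader might infer that a paired test always gains power, or always loses it when positives are rare. Neither holds: the loss at 15% v 5% and 10% v 5% with phi 0.3 belongs to the mid-p and exact versions, while ordinary McNemar gains there.

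**Conclusion.** The point holds as a minor error in the SAP's wording. Followed as written, the only categorical rule would analyse 34 pairs as 68 independent results; on any other reading the phase comparison of ETT categories has no test. Under assumed 30% positivity at both phases, the true rejection rate falls to 2.2% at phi 0.3 and 0.7% at phi 0.5. For a shift from 40% to 20% at phi 0.3, power is 45% with chi-square and 54% with ordinary McNemar. The argument for change is a test and interval that match the design; a power gain depends on the correlation. The sample size, the primary endpoint and the numbered secondary endpoints need no revision on this account.

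**What to change.** Keep a rule for independent groups and add one for the paired result, so that nothing is deleted by accident:

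- *Categorical data in independent groups, if any, are compared with the chi-square test.*
- *Categorical ETT results at the two phases are compared with a paired test: McNemar's test for positive versus not positive, and a marginal homogeneity test for the three-level result; discordant counts and the paired difference in proportions with a 95% CI are reported.*

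The version of McNemar's test should be fixed in advance. If mid-p is chosen and the software lacks it, it follows from the discordant counts b and c: with X binomial(b + c, 0.5), p = 2·P(X < min(b, c)) + P(X = min(b, c)) when b and c differ.

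The SAP should also say how the two cardiologists' readings become one category, since Protocol section 2 gives no rule for disagreement. It should say whether positive covers ECG-positive, clinically positive or both, and where indeterminate results go in the two-level comparison.

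The cost is a few sentences, with no new data, visits or patients. The downside is lower power if a woman's two results are uncorrelated: 42% v 46% for 40% v 20%, and 26% (ordinary) or 22% (mid-p) v 30% for 15% v 5%. With 34 women the comparison remains poorly powered for a small shift under any of these tests.
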